### 7.3.2. Classification of Exposure, Pregnancy, and Infant Outcomes

Exposure, pregnancy, and infant outcome variables ([Table 1](#)) are obtained by maternal report and/or medical record review as part of existing procedures for the OTIS/MotherToBaby Pregnancy Registry.

**Table 1 Exposure, Comparator and Outcome Variables**

Variable	Role	Data Source(s)	Operational Definition
Exposure to the Boostrix vaccine	Exposure	Maternal report, Vaccine record (e.g., yellow card), Medical record	Maternal report or medical record documentation of exposure to the Boostrix vaccine on or after the 1 st day of the 27 th week of pregnancy
Gestational timing of the Boostrix vaccine	Exposure	Maternal report Vaccine record (e.g., yellow card) Medical record	Maternal report or medical record documentation of the dates of the Boostrix vaccine administration on or after the 1 st day of the 27 th week of pregnancy
No Tdap vaccine exposure during pregnancy	Comparator	Maternal report Medical record	Maternal report of no exposure to any Tdap vaccine at any time from the first day of the LMP to the end of pregnancy; no documentation of Tdap vaccine in medical record
Preterm delivery	Primary Outcome	Maternal report Medical record	Maternal report and medical record documentation of a spontaneous or induced delivery after the 1 st day of the 27 th week of gestation or date of Boostrix vaccination, (whichever comes later) and <37 gestational weeks (as counted from the first day of LMP) (See Section 7.3.1 for operational definition of LMP) ( CDC, 2021 )
Stillbirth	Primary Outcome	Maternal report Medical record	Maternal report and medical record documentation of a non-deliberate fetal death that occurs after the 1 st day of the 27 th week of gestation or date of Boostrix vaccination, (whichever comes later), but prior to delivery ( Prager, 2021 )
Small for gestational age infant	Primary Outcome	Maternal report Medical record	Maternal report and medical record documentation of birth size for liveborn infants born after the 1 st day of the 27 th week of gestation or date of Boostrix vaccine, whichever comes later) (weight, length, or head circumference) $\leq 10^{\text{th}}$ percentile for sex and gestational age using NCHS pediatric growth curves for full term infants. Prenatal growth curves specific to preterm infants are used for preterm infants ( Olsen, 2010 ; Schlaudecker, 2017 )
Preeclampsia / eclampsia	Secondary Outcome	Maternal report Medical record	Maternal report and medical record documentation of preeclampsia. Preeclampsia is defined as hypertension in conjunction with at least one of the following: proteinuria; thrombocytopenia; impaired liver function; renal insufficiency; pulmonary edema; or visual or cerebral disturbances. The disorder usually occurs after 20 weeks of pregnancy and worsens over time.

Variable	Role	Data Source(s)	Operational Definition
			Eclampsia is a life-threatening condition that is considered a complication of severe preeclampsia and characterized by coma and/or seizures that are unrelated to a preexisting brain condition. Onset of preeclampsia/eclampsia as an outcome for this study is defined as onset after the 1 st day of the 27 th week of gestation or Boostrix vaccination date (whichever comes later).
Premature rupture of the membranes (PROM)	Secondary Outcome	Maternal report Medical record	Maternal report and medical record documentation of premature rupture of the membranes (amniotic sac). Premature rupture of the membranes is before labor begins on or after the 1 st day of the 27 th week of gestation or date of Boostrix vaccination (whichever comes later) and prior to 37 weeks' gestation.
Chorioamnionitis	Secondary Outcome	Maternal report Medical record	Maternal report and medical record documentation of chorioamnionitis. Chorioamnionitis classified using Brighton collaboration definition ( Kachikis, 2019 ) Please refer to details in Appendix 1
Neonatal sepsis of early onset	Secondary Outcome	Maternal report Medical record	Maternal report and medical record documentation of neonatal sepsis. Sepsis defined as isolation of pathogenic species from blood or cerebrospinal fluid culture within 72 hours of birth and antibiotic treatment for at least 5 days or until death (provisional definition pending confirmation of the ability to implement extraction in medical records)
Neonatal intensive care (NICU) for bronchopulmonary dysplasia	Secondary Outcome	Maternal report Medical record	Maternal report and medical record documentation of NICU care for bronchopulmonary dysplasia. Admission to the NICU defined as admission for any number of days for diagnosis of bronchopulmonary dysplasia
Neonatal death	Secondary Outcome	Maternal report Medical record	Maternal report and medical record documentation of neonatal death. Neonatal death defined as death of a live born infant within 28 days of birth

**Abbreviations:** CDC, Centers for Disease Control and Prevention; LMP, last menstrual period; NCHS, National Center for Health Statistics

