## Data Analysis

Demographic and other maternal characteristics will be compared between the two cohorts. The outcome analyses include:

1. comparison of proportion of PTBs among those enrolled prior to 37 weeks' gestation and resulting in a live born singleton infant between the *Boostrix*-exposed cohort and the comparison cohort by calculating hazard ratios and associated 95% confidence intervals.
2. comparison of proportion of stillbirths between the *Boostrix*-exposed cohort and the comparison cohort by calculating relative risks and associated 95% confidence intervals.
3. comparison of proportion of SGA infants ( $\leq 10^{\text{th}}$  centile for sex and gestational age) on birth weight, length, and head circumference among live born singletons between the *Boostrix*-exposed cohort and the comparison cohort by calculating relative risks and associated 95% confidence intervals.
4. comparison of proportion of preeclampsia/eclampsia diagnosed after the 1st day of the 27th week of gestation in pregnancies ending in livebirth or stillbirth between the *Boostrix*-exposed cohort and the comparison cohort by calculating relative risks and associated 95% confidence intervals.
5. comparison of proportion of cases of chorioamnionitis in pregnancies ending in livebirth or stillbirth between the *Boostrix*-exposed cohort and the comparison cohort by calculating relative risks and associated 95% confidence intervals.
6. comparison of proportion of PROM occurring after the 1st day of the 27th week of gestation in pregnancies ending in livebirth or stillbirth between the *Boostrix*-exposed cohort and the comparison cohort by calculating relative risks and associated 95% confidence intervals.
7. comparison of proportion of cases of neonatal sepsis occurring in pregnancies ending in live birth including twins or higher order multiples between the *Boostrix*-exposed cohort and the comparison cohort by calculating relative risks and associated 95% confidence intervals.

8. comparison of proportion of neonatal deaths occurring in pregnancies ending in live birth including twins or higher order multiples between the *Boostrix*-exposed cohort and the comparison cohort by calculating relative risks and associated 95% confidence intervals.

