### Study Objectives:

- The **primary objectives** of the study are to evaluate if there is an increased risk for preterm birth, small for gestational age infants, or stillbirth in pregnancies exposed to *Boostrix* vaccination on or after the 1st day of the 27th week of gestation when compared to a cohort of individuals unexposed to any Tdap vaccine during their pregnancy.
- The **secondary objectives** of the study are to evaluate if there is an increased risk of preeclampsia/eclampsia, premature rupture of the membranes, chorioamnionitis, neonatal sepsis, neonatal death, or neonatal intensive care admission for bronchopulmonary dysplasia in pregnancies exposed to *Boostrix* vaccination on or after the 1st day of the 27th week of gestation when compared to a cohort of individuals unexposed to any Tdap vaccine during their pregnancy.

These outcomes were selected based on the current knowledge on the safety of Tdap vaccination during pregnancy, adverse events reported into the Vaccine Adverse Event Reporting System (VAERS) and the biological plausibility for the exposure window of interest.

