**Table 3 Timing of Cohort Enrollment, Interviews, Examinations, and Medical Records**

	Any Time In Pregnancy	20-22 Weeks' Gestation 	32-34 Weeks' Gestation 	0-6 Weeks Post-Delivery	0-2 Months Post-Delivery
Referral 	√				
Enrollment and Consent 	√				
Enrollment Interview 	√				
Interim Interview I		√			
Interim Interview II			√		
Pregnancy Outcome Interview and Request for Medical Records				√	
Medical Record Acquisition and Review					√

 Participants may enroll in the study any time during pregnancy.

 If participant is enrolled and Intake Interview is conducted after 18 weeks' gestation, only one interim interview is conducted during pregnancy at 32-34 weeks gestation.

 If participant is enrolled and Intake Interview is conducted at 30 weeks' gestation or after, no Interim Interview is collected.

Medication or vaccine exposures entered into the database are coded using the Slone Drug Dictionary. Data are recorded on hard copies of forms and these records are retained by OTIS/MotherToBaby at the Research Center. These forms are considered the primary data sources for studies and can be adapted to add new data elements. Data from these forms are extracted and entered into a customized OTIS/MotherToBaby study database located in the Research Center.

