#### **7.5. Study size**

[figure not shown]
The target sample sizes in each of the study cohorts are as follows:

- 1,500 women exposed to *Boostrix* on or after the 1st day of the 27th week of gestation through the end of pregnancy
- 1,500 women unexposed to any Tdap vaccine throughout their pregnancy

Including an estimated 600 eligible participants per cohort already enrolled in the OTIS/MotherToBaby Pregnancy Registry, enrollment of 1,500 participants in each of the cohort groups is planned for completion within 4 years. Participants are eligible to enroll at any time in pregnancy including prior to the gestational timing of the recommended Tdap vaccine. (Examples of gestational timing of enrollment, exposure, and outcome are shown in [Figure 1](#) and [Figure 2](#)). Thus, some initially enrolled pregnancies will no longer be eligible for analysis due to pregnancy losses (spontaneous abortion, elective termination, stillbirth prior to the 27th week of gestation, or lost-to-follow-up). Additionally, some pregnancies will not be eligible for inclusion due to failure to release medical records. The final sample size of 1,500 per cohort will represent all pregnancies that met full inclusion/exclusion criteria. From this sample of livebirths and stillbirths, we conservatively estimate that at least 1,425 in each cohort will represent pregnancies ending in liveborn singleton infants.

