The primary analyses will be performed to estimate the causal relative risk using the method of inverse probability weighting (IPW) based on the PS. In the IPW approach, we will use stabilized weights that are further trimmed to be between 0.1 and 10 if necessary (Austin, 2015). The 95% CIs will be obtained using the bootstrap estimated variance and asymptotic normality, with 200 bootstrap samples.

A secondary analysis will be conducted using outcome regression, i.e., a logistic regression model will be fitted with the binary outcome (Y), and exposure (A) and propensity score (L) as regressors. Standardization will be performed to obtain the

estimated causal risk ratio (Hernán, 2019), which has the interpretation as the marginal or population averaged risk ratio. The CIs are obtained by bootstraps.

For the endpoint of **preterm delivery**, only pregnancies ending in delivery after the 1st day of the 27th week of gestation or the date of *Boostrix* vaccination (whichever comes later), enrolled prior to 37 weeks' gestation, and whose pregnancies result in a live-born singleton will be included in the analysis. Further, in the *Boostrix*-exposed group, exposure to vaccine must take place between the 1st day of the 27th week of gestation and before 36 weeks' and 5 days (allowing at least one day after vaccination for preterm delivery). Because women can meet criteria for eligibility for the study at arbitrary times following the 1st day of the 27th week of gestation, they may not be followed from the beginning of the relevant gestational age window. Those who experience the event prior to enrollment will never enter the study, leading to left truncation of the time to event. This can produce selection bias. In addition, vaccine exposure can occur on or any time after the 1st day of the 27th week of gestation in pregnancy, so exposure status is time-dependent. To address these issues, survival analysis methods will be used. Fleming-Harrington estimate at 37.0 weeks' gestation will be used to estimate the preterm delivery rate and 95% CI in each of the cohorts (Fleming, 1984; Pan, 1998). The Cox proportional hazards marginal structural model (MSM) incorporating time-dependent vaccine exposure and relevant covariates will be used to estimate the causal hazard ratio (HR) and 95% CI (Hernán, 2001).

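### PROM is capped at 37 weeks in Table 1 but not in the analysis list, and women vaccinated at or after 37 weeks stay in the exposed denominator

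*Protocol*

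**What the plan says.** - **Definition.** Table 1 (Protocol, Section 7.3.2) defines PROM as rupture before labor. It counts only rupture from the later of the first day of week 27 and the vaccination date "and prior to 37 weeks' gestation".
- **Analysis.** Item 6 of the data analysis list in the Abstract (Section 2) plans a "comparison of proportion of PROM occurring after the 1 st day of the 27 th week of gestation in pregnancies ending in livebirth or stillbirth". It states no upper limit. Section 7.7.1 has no text specific to PROM and Table 5 has no row for it, so item 6 is the only place where the protocol states the PROM comparison and its denominator.
- **Objectives.** Section 6 lists "premature rupture of the membranes, chorioamnionitis, neonatal sepsis, neonatal death, or neonatal intensive care admission for bronchopulmonary dysplasia" among the secondary outcomes. PROM is named without any time window.
- **Exposure and enrollment.** Section 7.5 counts exposure from the 27th "week of gestation through the end of pregnancy". Footnote 1 of Table 3 says "Participants may enroll in the study any time during pregnancy". The Abstract starts follow-up at vaccination for the exposed and at the first day of week 27 for the comparator.
- **The parallel endpoint.** For preterm delivery, Section 7.7.1 admits only pregnancies "enrolled prior to 37 weeks' gestation, and whose pregnancies result in a live-born singleton will be included in the analysis", and requires vaccination before 36 weeks and 5 days so that a preterm delivery can still follow it.

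**The concern.** A woman whose membranes rupture before labor at 38 weeks is a case under item 6 and not a case under Table 1. The protocol does not say which reading answers the secondary objective.

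The second problem arises if Table 1 is followed, as its role as the operational definition suggests. A woman vaccinated at 38 weeks begins follow-up after the PROM window has closed. She can add to the denominator and never to the numerator. Late vaccination exists only in the exposed cohort, so only the exposed proportion is lowered. In a safety study this bias can hide a harm or suggest a benefit. The protocol guards against it for preterm delivery, which has the same 37-week limit, but not for PROM.

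**Working it through.** The protocol gives no rate, sample size or power for PROM, so there is no PROM figure to reproduce. As a check on the method, exact two-sided Fisher power was computed for the chorioamnionitis row of Table 4 (1,469 per group, 3%, relative risk 1.7). It is 80.4%, against the stated 80%.

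**1. Who can be a case under Table 1**

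| Group | PROM window | In item 6's denominator? | Excluded for preterm delivery? |
|---|---|---|---|
| Exposed, vaccinated before 37 weeks | vaccination to 37 weeks | yes | only if vaccinated at 36 weeks 5 days or later, or enrolled at 37 weeks or later |
| Exposed, vaccinated at or after 37 weeks | empty | yes | yes |
| Comparator | first day of week 27 to 37 weeks | yes | only if enrolled at 37 weeks or later |

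**2. Effect on the relative risk**

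Let s_E and s_C be the shares of each cohort with an empty window. Then

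observed RR = true RR × (1 − s_E) / (1 − s_C).

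For late vaccination s_C = 0, so observed RR = true RR × (1 − s). The documents do not give s; the values below are assumptions.

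| s | true RR 1.0 appears as | true RR 2.0 appears as |
|---|---|---|
| 2% | 0.98 | 1.96 |
| 5% | 0.95 | 1.90 |
| 10% | 0.90 | 1.80 |

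**3. Effect on power**

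Section 7.5 expects the secondary endpoints outside Table 4, which include PROM, to be below 1-2% in the comparator. Exact Fisher power (two-sided alpha 0.05, 1,500 per cohort) for a true relative risk of 2.0, with the cohort size held fixed so that only the dilution shows:

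| Comparator rate | s = 0 | s = 5% | s = 10% |
|---|---|---|---|
| 2% | 88.2% | 81.6% | 72.9% |
| 1% | 56.5% | 48.5% | 40.5% |

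**4. Enrollment at or after 37 weeks**

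Table 1 does not require rupture after enrollment. A woman whose membranes ruptured at 36 weeks and who is still pregnant when she enrolls at 37 weeks would count. What is lost are women who had early PROM and delivered before they could enroll. That is left truncation and can occur in both cohorts. Equal shares cancel in the formula (10% in each gives 0.90/0.90 = 1.00); unequal shares shift the result either way.

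**5. Why exclusion alone is not enough**

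A woman vaccinated at 36 weeks and 4 days has 3 days at risk before 37 weeks. A comparator followed from 27 weeks has 37 − 27 = 10 weeks (11 if the 27th week is taken to begin at 26 completed weeks). A plain comparison of proportions treats these as equal.

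**The case against.** - **Item 6 is a shortened abstract line.** It also omits the vaccination date as an alternative start, and item 1 omits the vaccination limit for preterm delivery. Table 1 is the only explicit definition and probably the intended one. This is fair, and it makes the mismatch look more like an omission than a second deliberate endpoint. It does not help the denominator, because Table 1 is the reading under which late-vaccinated women have an empty window.
- **The SAP may settle it.** Section 7.3 leaves detailed definitions to the SAP, and Section 7.7.3 says each outcome has its own set of subjects. Neither statement withdraws the denominator written in item 6, and a SAP cannot follow both texts.
- **The bias may be small.** The Abstract and Section 5.1 give 27-36 weeks as the preferred time for Tdap, so s may be low. At 1-2% there would be about 15 to 30 events per cohort (1,500 × 0.01 and 1,500 × 0.02). Near the null the 95% interval then spans a factor of about exp(1.96 × √(2/15)) = 2.0 to exp(1.96 × √(2/30)) = 1.7 either way. A shift to 0.90-0.98 is small beside that. This stands as a limit on importance. Still, the shift is systematic, runs in one direction and can be avoided.

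Three stronger readings are tempting but unsupported. A reader might infer that the objectives contradict Table 1. They do not: the week-27 phrase there qualifies vaccination, and PROM carries no timing. A reader might also infer that women enrolled at or after 37 weeks can never be cases; step 4 of the working shows otherwise. Nor can the ratio of events under the two definitions be stated, because the protocol does not give the share of PROM that occurs before 37 weeks.

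**Conclusion.** The point holds in two parts. First, Table 1 caps PROM at 37 weeks and item 6 does not, so the protocol carries two case definitions under one name. Second, under Table 1 women vaccinated at or after 37 weeks cannot be cases but remain in the exposed denominator, whereas the protocol removes such women for preterm delivery.

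This multiplies the relative risk by (1 − s): a true 1.0 appears as 0.98 to 0.90 for an assumed s of 2% to 10%. The direction, toward apparent safety, is certain for late vaccination; the size depends on a share the documents do not give. The left truncation from late enrollment is a separate problem whose direction is not established. PROM is a secondary endpoint with few expected events, so this warrants correction before analysis but does not threaten the study as a whole.

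**What to change.** Use one PROM definition throughout.

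- **If the 37-week cap is kept:** call the endpoint preterm PROM wherever it is named as an objective and in item 6. Limit its analysis set to women enrolled before 37 weeks and, if exposed, vaccinated before 37 weeks, and end follow-up at 37 weeks. Analyse it with the delayed-entry, time-dependent-exposure method already planned for preterm delivery. Only the timing limits need carrying over, not the restriction to live-born singletons. Report how many women the rule removes: most late-vaccinated women will have reached vaccination free of PROM, so removing them is not neutral.
- **If the cap is dropped:** delete it from Table 1 and report PROM before 37 weeks as a subset analysed with the same restriction. Dropping the cap removes the empty windows but not the shorter follow-up of women vaccinated late.

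The cost is a few wording edits, one analysis-set rule and, where the restriction applies, a slightly smaller PROM denominator. No new data collection is needed, since vaccination date and gestational age at enrollment are already captured.

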### 7.3.3. Demographics and Clinical Characteristics

Potential confounders and other covariates to be collected include maternal age, race/ethnicity, pre-pregnancy body mass index, socioeconomic status, pregnancy and health history, lifestyle factors, comorbidities, medication, vaccine and vitamin/mineral exposures, and prenatal tests. [Table 2](#) provides a description of corresponding variables to be included in this study. The SAP will provide greater detail on covariable definitions.

**Table 2 Demographic and Clinical Variables, Maternal and Paternal age**

Variable	Role	Data Source(s)	Operational Definition
Maternal Age (years)	Confounder	Maternal report	Maternal age (years) at due date, continuous and categorical (<25, 25-29, 30-34, >34).
Paternal Age (years)	Confounder	Maternal report	Paternal age (years) at due date, continuous and categorical (<25, 25-29, 30-34, >34).
Maternal Race	Confounder	Maternal report	Maternal (Caucasian/White, Black, Asian/Pacific Islander, Native American, Other).
Maternal Ethnicity	Confounder	Maternal report	Maternal (Hispanic, Non-Hispanic).
Maternal Education	Confounder	Maternal report	Maternal Educational Category (years of completed education <12, 12-15, >15).
Socioeconomic Category	Confounder	Maternal report	Hollingshead Socioeconomic Category based on maternal and paternal occupation and education (1-5).
Maternal Height	Confounder	Maternal report	Maternal height (cm)
Maternal Pre-pregnancy body weight	Confounder	Maternal report	Maternal pre-pregnancy body weight (kg)
Maternal Pre-pregnancy body mass index	Confounder	Maternal report	Maternal pre-pregnancy BMI (<18.5, 18.5-24.9, 25-29.9, >=30)
Number of times pregnant	Confounder	Maternal report Medical record	Number of times ever pregnant (1, 2-3, 4-5, >=6) (confirm with medical record)
Previous live birth or stillbirth deliveries	Confounder	Maternal report Medical record	Number of previous live birth or stillbirth deliveries (0, 1-2, 3-4, >=5) (confirm with medical record)
Previous pregnancies ending in spontaneous abortion	Confounder	Maternal report Medical record	Number of previous pregnancies ending in spontaneous abortion (0, 1, 2, >=3) (confirm with medical record)
Previous pregnancies ending in elective termination	Confounder	Maternal report Medical record	Number of previous pregnancies ending in elective termination (0, 1, 2, >=3) (confirm with medical record)
Previous pregnancies ending in preterm birth	Confounder	Maternal report Medical record	Number of previous pregnancies ending in preterm birth (confirm with medical record if available)
Previous pregnancies ending in growth restricted infant	Confounder	Maternal report Medical record	Number of previous pregnancies ending in infant with intrauterine growth restriction (confirm with medical record if available)
Gestational age at study enrollment	Confounder	Maternal report	Weeks of pregnancy at time of enrollment, continuous and categorical ( $\leq 13$ , 13.1-19.9, $\geq 20$ ): gestational age is calculated from the first date of LMP
Referral source	Confounder	Maternal report	Source options: Sponsor, OTIS service, health care provider, Internet, Other.
Prenatal, Multivitamin, or Folic acid	Confounder	Maternal report	Prenatal, Multivitamin or Folic Acid supplement use by timing (began prior to conception, post-conception only, not taken at all)
Alcohol use in pregnancy	Confounder	Maternal report	Yes/No. Dose and frequency are captured

Variable	Role	Data Source(s)	Operational Definition
Tobacco use in pregnancy	Confounder	Maternal report	Yes/No. Dose and frequency are captured
Medication and vaccine use in pregnancy	Confounder	Maternal report	Prescription and over-the-counter medications, vaccines are captured for the period from the first day of LMP through the end of pregnancy; dose, frequency, duration, and indication including stop and start dates are collected
Maternal pregnancy exposure to a known human teratogen	Confounder	Maternal report	Maternal pregnancy exposure to a known human teratogen
Comorbid maternal medical history	Confounder	Maternal report Medical record	Comorbid maternal medical history (e.g., chronic hypertension, asthma)
Current pregnancy ending in a major birth defect	Confounder	Maternal report Medical record	A major structural or chromosomal defect that has either cosmetic or functional significance to the child (e.g., a cleft lip) classified using CDC coding criteria

Methods for identifying and controlling for these confounders and/or effect modifiers are described in Section 7.7.1. The SAP will provide greater detail on the definitions of, the identification of and the controlling for confounders and/or effect modifiers.

